5.2 Study Treatments

5.2.1 Extent of Exposure

Extent of treatment exposure for completed or discontinued subjects will be calculated in days using the following:

$$\text{Extent of Exposure (days)} = \text{Date of last dose} - \text{date of first drug dosing} + 1$$

Extent of treatment exposure for subjects who were lost to follow-up will be calculated in days using the following:

$$\text{Extent of Exposure (days)} = \text{Date of last recorded visit} - \text{date of first drug dosing} + 1$$

Extent of treatment exposure (days) for each subject exposed to study drug will be summarized with continuous descriptive statistics for each treatment group, using the Safety population. A subject listing of treatment exposure will also be produced.

5.2.2 Treatment Compliance

Subjects will be instructed on proper instillation and storage of study drug at the end of Visits 1, 2, 3, 4 and 5, and given written instructions. The used and unused study drug vials will be collected at each visit from Visit 2 up to and including Visit 6 to assess dosing compliance. Dosing compliance will be based on the used and unused vial count. If the subject is less than 80% or more than 125% compliant with dosing based on the expected number of used vials, then the subject will be deemed non-compliant and a deviation should be recorded.

Dosing compliance (% compliance) will be assessed by calculating the number of doses taken and comparing that to the number of doses expected as follows:

$$\text{Compliance (\%)} = \frac{\text{Number of Doses Taken}}{\text{Number of Doses Expected}} \times 100\%$$

The number of doses taken by week will be calculated from the number of used vials on the drug accountability case report form (CRF). The number of doses taken in total will be calculated from the number of drug administered in diary. The planned drug use is calculated as (daily drug use specified in the protocol) \times (the number of days between the 2 study visits). If a randomized subject discontinues from the study on Day 1, the number of doses expected will be 1. Otherwise, the number of doses expected will be calculated as $2 \times$ (the Study Day of the last dose - the Study Day of the first dose +1) if discontinued, and $2 \times$ (the Study Day of the visit 6 - the Study Day of the first dose) if completed for all subjects.

Dosing compliance (%) will be summarized with continuous descriptive statistics for each treatment group using the Safety population. A categorical dosing compliance variable will also be derived as non-compliant (<80% or >125%) or compliant (\geq 80% and \leq 125%) and summarized with discrete summary statistics. Under-compliance (<80%) and over-compliance (>125%) will also be separately summarized.

A subject listing of dosing compliance will also be produced.

6. Efficacy Analysis

6.1 Analysis Specifications

6.1.1 Level of Significance

All statistical testing will be two-sided with a significance level of 0.05 ($\alpha = 0.05$) unless otherwise specified. Confidence intervals (CI) for differences between treatment groups

will be two-sided at 95% confidence levels where appropriate. All p-values will be rounded to four decimal places; p-values less than 0.0001 will be presented as “<0.0001”; p-values greater than 0.9999 will be presented as “>0.9999”.

6.2 Primary Efficacy Endpoint

The primary efficacy endpoint is inferior corneal staining (sign), Pre- to Post-CAE at Day 57.

6.2.1 Definition

For the primary efficacy endpoint, the pre- to post-CAE[®] ICSS change will be calculated as post-CAE[®] ICSS– pre-CAE[®] ICSS, noted as Δ ICSS. The change from baseline in Δ ICSS will be calculated as visit (Δ ICSS) – baseline (Δ ICSS) (denoted as $\Delta\Delta$ ICSS). Treatment comparisons between treatment and placebo groups will be calculated as treatment – placebo (denoted as $\Delta\Delta\Delta$ ICSS). A negative value indicates a better outcome for the treatment group (i.e., the treatment group increase more or worsen less in dry eye signs or symptoms than the placebo group).

6.2.2 Analysis Methods

An ANCOVA model will be used to compare $\Delta\Delta$ ICSS at Day 57 (Visit 6) (measured by the Ora Calibra[®] scale), between HBM9036 and placebo. The ANCOVA model will include treatment and baseline Δ ICSS as the only 2 covariates. The between-group differences in $\Delta\Delta$ ICSS, two-sided 95% confidence intervals (CIs), and p-value will be reported.

Two-sample t-test will be conducted as a sensitivity analysis.

The primary analysis will be performed on the PP populations. After obtaining data sets and calculating changes from baseline, the following SAS code will be used to run the ANCOVA model on data sets:

```
PROC MIXED DATA = OUTDATA;  
  CLASS TREATMENT;  
  MODEL CHANGE_INFERIOR = BASELINE TREATMENT / SOLUTION COVB;  
  LSMEANS TREATMENT / CL PDIFF;  
  ODS OUTPUT LSMEANS = OUTLS DIFFS = OUTDIFFS;  
RUN;
```

where

- *TREATMENT* is the name of the treatment group variable
- *BASELINE* is the baseline post-CAE[®] – pre-CAE[®] inferior corneal staining score in the study eye
- *CHANGE_INFERIOR* is the post-CAE[®] – pre-CAE[®] inferior corneal staining score in the study eye at Visit 6 (Day 57 ± 3) – *BASELINE*

Sensitivity analyses will be performed:

- on the FAS population using the last observation carried forward (LOCF) - imputation method for missing values will be used which means the last value from the previous visits will be carried forward, matching pre-CAE[®] or post-CAE[®] time points and a pre-CAE[®] time point will never be imputed for a post-CAE[®] value, and vice versa to have a full accounting of the FAS at the Day 57
- on the FAS using MMRM methodology

An example of the SAS code implementation of the ANCOVA model for the FAS population using LOCF is as follows:

```
PROC MIXED;  
    CLASS TREATMENT;  
    MODEL CHANGE_INFERIOR = BASELINE TREATMENT / SOLUTION COVB;  
    LSMEANS TREATMENT / CL PDIFF;  
RUN;
```

For LOCF, baseline value will be used for post baseline if both visit 5 and visit 6 are missing.

An example of the SAS code implementation of the ANCOVA model for the MMRM is as follows:

```
PROC MIXED;  
    CLASS TREATMENT PTNO VISIT;  
    MODEL CHANGE_INFERIOR = BASELINE TREATMENT VISIT VISIT*BAELINE  
    VISIT*TREATMENT/ DDFM=KR SOLUTION CHISQ;  
    REPEATED VISIT/SUBJECT=PTNO TYPE=UN R RCORR;  
    LSMEANS TREATMENT*VISIT / PDIFF=ALL OM CL ALPHA=0.05 SLICE=VISIT;  
RUN;
```

where

- *PTNO* is Patient number (ID)
- *VISIT* is visit timepoint (5, 6)
- *VISIT*BAELINE* is the Visit*Baseline interaction term
- *VISIT*TREATMENT* is the Visit*Treatment interaction term

Mean changes from baseline will be analyzed using a restricted maximum likelihood (REML) based repeated measures approach. Analyses will include the fixed, categorical effects of treatment, visit and treatment-by-visit interaction, as well as the continuous,

fixed covariates of baseline and baseline-by-visit interaction. An unstructured covariance structure will be used to model the within-patient measurement.

If a patient misses a visit, the missing data will not be imputed. The mixed effect model will handle missing data based on a likelihood method under the “missing at random” assumption.

Pre-CAE[®] to post-CAE[®] inferior corneal staining changes from baseline in the study eye will be displayed graphically by day and visit in a line plot by treatment group.

6.3 Secondary Efficacy Endpoints

Continuous and ordinal secondary efficacy variables collected at the specific visit will be summarized descriptively (n, mean, standard deviation, median, min and max). Change scores from pre- to post-CAE[®] will be calculated as post-CAE[®] – pre-CAE[®] score. The change from baseline will be calculated as visit – baseline. Two-sample t test and an ANCOVA model adjusting for baseline will also be assessed where appropriate. No imputation will be performed for secondary efficacy endpoints.

Tear film break-up time (TFBUT), conjunctival redness score, unanesthetized schirmer’s test result, ocular discomfort scale and visual analogue scale will be summarized by visit, time point, and treatment group using quantitative summary statistics. Changes from baseline will be compared between treatment groups using ANCOVA model that adjust for baseline. The differences in means, two-sided 95% confidence intervals (CIs) for the difference in means will be reported. Analyses will be performed on the PP population with observed data only.

Ocular discomfort and dry eye symptoms will be recorded by both visit and daily diary. For visit summary, quantitative summary statistics will be used as above. For diary summary, the average of the morning and evening assessments will be calculated for each day and symptom. Changes from baseline in weekly average scores at week 8 will be compared between treatment groups using ANCOVA model that adjust for baseline. The differences in means, two-sided 95% confidence intervals (CIs) for the difference in means will be reported. Analyses will be performed on the PP population with observed data only. Changes from baseline in weekly average scores of ocular discomfort, each individual symptom will be displayed graphically by week in a line plot by treatment group.

The OSDI[®] is assessed on a scale of 0 to 100, with higher scores representing greater disability.

The total OSDI[®] score is calculated by the following:

$$\text{OSDI}^{\circledR} = \frac{(\text{sum of scores}) \times 25}{\# \text{ of questions answered}}$$

Note that the number of questions answered in the denominator should exclude those questions with a response of “N/A”. Continuous descriptive statistics, including 95% CIs, as well as changes from baseline will be summarized by treatment group and visit.

Changes from baseline in total OSDI[®] score will be compared between treatment groups using ANCOVA model that adjust for baseline. The differences in means, two-sided 95% confidence intervals (CIs) for the difference in means will be reported. Analyses will be performed on the PP population with observed data only.

7. Safety Analysis

Adverse events (AE) will be coded using the Medical Dictionary for Regulatory Authorities (MedDRA). Summary will focus on treatment-emergent AE (TEAE), which is defined as AE that occur or worsen after the first dose of study treatment. Frequencies and percentages of subjects with TEAEs, serious TEAEs, and TEAEs causing premature discontinuation will be provided by treatment group. Furthermore, frequencies will be given of subjects with TEAEs by system organ class, by system organ class and preferred term.

7.1 Adverse Event

An overall summary will be presented that includes the number of AEs, serious AEs (SAE), TEAEs and serious TEAEs (TE-SAE). The summary will also include the number and percentage of subjects withdrawn due to an AE, the number and percentage of subjects with an AE resulting in death, and the number and percentage of subjects who experienced at least one TEAE, SAE and TE-SAE, by treatment group and for all subjects. This summary will include breakdowns of AEs further categorized as ocular or non-ocular. The summary will also include the number and percentage of resolved ocular AEs, and the mean number of days until AE resolution for resolved ocular AEs. AEs recorded in the eCRF which began prior to treatment will not be included in the summary tables but will be included in the AE data listings. All AEs will be coded using MedDRA Version 22.

Treatment-emergent adverse events (TEAEs) are defined as any adverse event that occurs or worsens from the first dose of study treatment (at visit 2) to last dose+7 day. Additional summaries of TEAEs will be provided showing the number and percentage of subjects who experienced at least one TEAE. These summaries will be presented by SOC and PT. Non-ocular TEAEs will be summarized using discrete summary statistics and presented by treatment group at the subject level by SOC and PT. Ocular TEAEs will also be

similarly summarized at the subject level. If a subject reports the same PT multiple times within the same SOC, that PT will only be reported once within that SOC. In the summary, SOC will be listed in order of descending frequency by study active treatment for all subjects; PTs will be listed in order of descending frequency for all subjects within each SOC. The occurrence of non-ocular and ocular TEAEs will also be tabulated by SOC, PT, and maximal severity.

Separate summaries will be provided for the following categories of AEs:

- Ocular TEAEs
- Non-ocular TEAEs
- Treatment-related ocular TEAEs
- Treatment-related non-ocular TEAEs
- SAEs

Severity of an adverse event is defined as a qualitative assessment of the degree of intensity of an adverse event as determined by the investigator or reported to him/her by the patient/subject. Summaries of TEAEs by maximal severity will be presented for ocular AEs and non-ocular AEs separately. The number of subjects with any TEAEs (along with percentages) will be tabulated by SOC and PT within each SOC by treatment group. To count the number of subjects with any TEAEs, if a subject has multiple TEAEs coded to the same PT within the same SOC, the subject will be counted once under the maximal severity. All probable, unclassified, and definite TEAEs are considered as treatment-related TEAEs. All AEs will be presented in a subject listing.

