1.4 Previous Clinical Studies

1.4.1 Phase I Study

A first-in-human study was completed in Korea in August 2016 aiming to assess the safety, local tolerance, and PK properties of HBM9036. A total of 77 subjects were screened and 20 subjects were randomized to Group A and Group B to receive topical ophthalmic instillation of HBM9036 0.5 mg/mL and 5 mg/mL twice in one day into left eyes, while right eyes received vehicle placebo.

Of the 20 subjects who received study drugs, 11 subjects reported 27 AEs. Twenty AEs were mild in severity and the subjects recovered without sequela. The remaining 7 AEs were moderate in severity, and all events were reported by one subject. Among the 7 moderate AEs, all symptoms except for corneal opacity resolved completely. The assessment of causal relationship between the study drug and the 7 AEs was determined to be “unlikely” for all events. The most frequently reported AE after administration of the study drug was conjunctival hyperemia, with 18 events reported. There were 5 AEs reported by 2 subjects from the HBM9036 0.5 mg/mL group and 6 AEs reported by 3 subjects from the HBM9036 5 mg/mL group. The remaining 7 AEs were reported by 3 subjects in the placebo group. There were 24 AEs reported by 9 subjects (45%) that may have been caused by the study drug (the causal relationship was possible, probable, or certain). Among the AEs thought to be caused by the study drug in each group, conjunctival hyperemia was the most frequently reported (17 AEs reported by 7 [35.0%] subjects). All conjunctival hyperemia events were mild, and the subjects recovered without sequelae. There was no serious AE or unexpected adverse drug reaction reported, and no clinically significant changes were observed in vital signs, physical examinations, and medical laboratory tests. Local tolerance was assessed and there were no moderate or severe ophthalmologic symptoms observed.

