7.2.7.2 Post-Study Follow-Up of Adverse Events

Any AEs that are unresolved at the subject's last study visit need to be followed up by the Investigator until clinical signs/symptoms disappear or return to baseline level, or become stable at the Investigator's discretion, or refusal to follow-up by subjects, or lost to follow-up. Harbour BioMed reserves the right to request additional information for any subject with ongoing AE(s)/SAE(s) at the end of the study, if judged necessary.

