8 STUDY PLAN

8.1 Schedule of Study

See Table 1.

Table 1. Schedule of Study

Procedure	Visit 1 Day -13 ± 2		Visit 2 Day 1		Visit 3 Day 8 ± 1	Visit 4 Day 15 ± 2	Visit 5 Day 29 ± 2		Visit 6 Day 57 ± 3		EOT ⁴	FU ²
	Before CAE	After CAE	Before CAE	After CAE	No CAE	No CAE	Before CAE	After CAE	Before CAE	After CAE		
Informed consent	X											
Medical/medication history and demographics	X											
Medical/Medication history update			X		X	X	X		X			
Placebo run-in dispensation		X										
Placebo run-in collection			X									
Randomization				X								
Study drug dispensation				X		X		X				
Study drug instillation				X	X							
Study drug collection					X	X	X		X		X	
Diary dispensation		X		X	X	X		X				
Diary collection			X		X	X	X		X		X	
Review of inclusion/exclusion criteria	X	X	X	X								
Adverse event Query	X	X	X	X	X	X	X	X	X	X	X	X
Urine pregnancy test	X ¹								X ¹		X ¹	
Drop tolerance assessment				X								
Ora Calibra® Ocular Discomfort Scale	X	X	X	X	X	X	X	X	X	X		
Ora Calibra® Ocular Discomfort and 4-Symptom Questionnaire	X	X	X	X	X	X	X	X	X	X		
VAS Discomfort Scale	X	X	X	X	X	X	X	X	X	X		

Procedure	Visit 1 Day -13 ± 2		Visit 2 Day 1		Visit 3 Day 8 ± 1	Visit 4 Day 15 ± 2	Visit 5 Day 29 ± 2		Visit 6 Day 57 ± 3		EOT ⁴	FU ²
	Before CAE	After CAE	Before CAE	After CAE	No CAE	No CAE	Before CAE	After CAE	Before CAE	After CAE		
OSDI [®] Questionnaire	X		X		X	X	X		X			
Visual acuity (ETDRS)	X		X		X	X	X		X		X	
Slit-lamp bio-microscopy	X	X	X	X	X	X	X	X	X	X	X	
Conjunctival redness	X	X	X	X	X	X	X	X	X	X		
TFBUT	X	X	X	X	X	X	X	X	X	X		
Fluorescein staining	X	X	X	X		X	X	X	X	X		
CAE exposure	X		X				X		X			
Discomfort grading during CAE exposure	X		X				X		X			
Schirmer's test		X		X		X		X		X		
Intraocular pressure		X								X	X	
Fundus color photography ³		X								X	X	
Subject withdrawal from the study										X		

EOT: End of Treatment

1. Applies to females of child bearing potential. See the definition for details.
2. A telephone follow-up will be made 7 days after the last dose of study drugs to collect safety information. See Section 8.4 for details.
3. If retinopathy is detected, or if it is impossible to take clear photos of both optic discs and macula lutea simultaneously, the indirect ophthalmoscope or preset lens should be inspected under the pupil dilation conditions.
4. The examination that a subject who withdraws the study must receive. See Section 8.3 for details.

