8.4 End of Study

All subjects will be followed up by telephone call 7 days after last dose of study drug. The following procedures will be completed:

- Review ongoing AEs and SAEs (if any);
- Collection of new SAEs (if any);
- Review of concomitant medications.

Note: For the subjects who withdraw the informed consent, a telephone follow-up will be made at least 7 days after last dose of study drug.

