9.5.2 Safety Analysis

Frequencies and percentages of subjects with treatment-emergent adverse events (TEAEs), serious TEAEs, and TEAEs causing premature discontinuation will be provided by treatment group. An AE is treatment emergent if it 1) occurs after the first dose of randomized study treatment or 2) if it is present prior to receipt of randomized study treatment but worsens in severity or increases in frequency after the first dose of randomized study treatment. Frequencies and percentages of subjects with AEs, SAEs, and AEs causing premature discontinuation will be provided by treatment group. The AEs will be listed by MedDRA SOCs and PTs and the AE listings will be categorized by severity, the causal relationship with study drug, and whether the AEs leading to discontinuation of study. No hypothesis test will be performed. Separate analyses will be performed for ocular specific and all AEs (including systemic).

Other safety endpoints including visual acuity, slit-lamp biomicroscopy, fundus color photography, drop tolerance, and intraocular pressure, will be summarized by treatment group and visit using descriptive statistics. Changes from baseline will also be summarized where appropriate. For assessments performed by eye, study eye and fellow eye will be summarized separately. In addition, shifts from baseline to worst on-treatment value will be summarized.

The exposure time (number of days) and drug administration times will be summarized by treatment group. The number and percentage of subjects with compliance will be calculated. The total exposure of the safety population will be summarized based on actual treatment received.

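### SAP 7.1 summarises ocular AE duration only among AEs that resolved, so unresolved events drop out and the between-arm comparison of duration can be biased

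*SAP*

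**What the plan says.** The overall AE summary in SAP 7.1 has two items on resolution of ocular events. The first is a count: "The summary will also include the number and percentage of resolved ocular AEs". The second is a duration: "the mean number of days until AE resolution for resolved ocular AEs". Section 7 of the SAP plans no median, no censored estimate and no cut-off date for recording resolution. The same section adds a safeguard: "All AEs will be presented in a subject listing".

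Three protocol provisions determine how complete the resolution dates will be.

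- Section 7.2.7.2: AEs open at the last study visit "need to be followed up by the Investigator until clinical signs/symptoms disappear or return to baseline level". Follow-up may also stop when the event is judged stable, or when the subject refuses or is lost. There is no calendar limit.
- Table 1 in section 8.1, footnote 2: "A telephone follow-up will be made 7 days after the last dose of study drugs to collect safety information". Section 8.4 has ongoing AEs reviewed at that call. It falls at about Day 64 for a subject who completes treatment.
- Section 9.5.2, on the AE summaries: "No hypothesis test will be performed".

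**The concern.** A mean taken only over resolved events conditions on the outcome being measured. Unresolved events are left out however long they have lasted. If ascertainment is cut short, an event that starts late in the eight weeks is counted only if it resolves quickly. The two arms' means are then taken over differently selected events and do not compare how long ocular reactions last.

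Ocular tolerability is a place where the arms could differ. Protocol 1.4.2 reports eight withdrawals for allergic conjunctivitis in the US Phase II study, 3 on 0.10% and 5 on 0.25%; these add up to all eight, so none was on placebo. Unresolved ocular events are also possible. Protocol 1.4.1 reports of Phase I: "Among the 7 moderate AEs, all symptoms except for corneal opacity resolved completely". That example should be read with its context: all seven events were in one subject, causality was rated unlikely, one eye received drug and the other placebo, and the text does not say which eye was affected.

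At stake is one descriptive line in the safety summary.

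**Working it through.** The documents state no AE duration or resolution rate, so there is no plan figure to reproduce. Everything below is illustration on stated assumptions.

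**Model.** Durations T are exponential with mean m. Onset is uniform over Days 1 to 57. Ascertainment stops at Day 64. Follow-up per event is then uniform from a = 7 to b = 63 days.

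- I0 = m(e^(−a/m) − e^(−b/m)) / (b − a)
- I1 = [(ma + m²)e^(−a/m) − (mb + m²)e^(−b/m)] / (b − a)
- Share resolved = 1 − I0
- Mean among resolved = (m − m·I0 − I1) / (1 − I0)

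**True mean 14 days.** I0 = 14(0.6065 − 0.0111)/56 = 0.149. I1 = (294 × 0.6065 − 1078 × 0.0111)/56 = 2.97. Share resolved 85%. Reported mean = (14 − 2.08 − 2.97)/0.851 = 10.5 days.

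**True mean 30 days.** I0 = 30(0.7919 − 0.1225)/56 = 0.359. I1 = (1110 × 0.7919 − 2790 × 0.1225)/56 = 9.60. Share resolved 64%. Reported mean = (30 − 10.76 − 9.60)/0.641 = 15.0 days.

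A true ratio of 30/14 = 2.1 appears as 15.0/10.5 = 1.4.

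**Sensitivity to the cut-off and to onset (same formulas).**

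| Case | a to b (days) | True mean 14 | True mean 30 |
|---|---|---|---|
| Cut-off Day 64 | 7 to 63 | 10.5 | 15.0 |
| Cut-off Day 78 | 21 to 77 | 12.0 | 18.2 |
| Cut-off Day 244 | 187 to 243 | 14.0 | 29.8 |
| Cut-off Day 64, onset Days 1–15 | 49 to 63 | 12.9 | 19.7 |

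With long follow-up, and every event eventually resolving, the bias all but vanishes.

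**Events that never resolve.** Take onset uniform over Days 1–56 and cut-off Day 64, so a = 8 and b = 63. Placebo events have mean 10 days. On drug, 20% never resolve and the rest match placebo.

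- The resolved-only means are identical, 8.4 and 8.4 days.
- The shares resolved are 92% and 0.8 × 92% = 74%.
- The median times to resolution, which Kaplan-Meier recovers, are 10 ln 2 = 6.9 days on placebo and 10 ln(0.8/0.3) = 9.8 days on drug.

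**Unequal follow-up (same onset and cut-off unless stated).**

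- True means 10 (placebo) and 20 (drug), with drug events followed for only 7 days: the drug mean is (20 − 27e^(−0.35))/(1 − e^(−0.35)) = 3.3, against 8.4 on placebo. The direction reverses.
- Equal true means of 10, with placebo events followed for at most 14 days: simulation gives 5.3 on placebo and 8.4 on drug, a spurious excess of 3.1 days on drug.

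**Likely number of events.** In the US Phase II study 44 subjects were 29.3%, so the safety population was about 44/0.293 = 150. Its 26 ocular TEAEs scale to 26/150 × 50, or about 9 per arm here, if rates are similar. With 9 uncensored exponential events of mean 14 days, the sample median has a 95% range of roughly 3 to 22 days.

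**The case against.** The main objection is that Day 64 is only the last scheduled contact. Protocol 7.2.7.2 keeps open AEs under follow-up without a calendar limit, and the SAP's limit of seven days after last dose defines which events are treatment-emergent, not when a resolution may be recorded. This stands, and it removes most of the bias for events that do resolve. It does not help with events that stabilise without resolving, end in refusal or loss, or are open at database lock.

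A reader might infer that the plan understates any difference in duration, or makes the arms look alike. The documents do not support either reading. The number and percentage resolved appear with the mean; in the illustration above the reader would see 85% against 64% beside 10.5 against 15.0 days, both pointing the same way. In the never-resolving case the percentages are 92% against 74%. With unequal follow-up the bias can reverse or exaggerate a difference. Nor are unresolved events necessarily the longest, since one with late onset may have been short so far.

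There is other evidence on persistence: the AE listing, and in SAP 7.2 slit-lamp results by visit and eye with shift tables against baseline, with the cornea among the structures examined (Protocol Appendix 1). A persistent corneal finding could therefore be seen elsewhere. What remains is that neither these outputs nor the percentage resolved summarises by arm how long unresolved events have lasted, and they do not make a comparison of the two means valid.

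Kaplan-Meier has limits too. Events will be few, several may come from one subject, and censoring at stabilisation is informative.

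**Conclusion.** The point holds as a minor one. The only planned summary of ocular AE duration leaves out events that have not resolved by last contact, so the between-arm comparison of duration can be biased. Direction and size depend on how long events are followed in each arm and on the share that never resolve. If follow-up is completed and all events resolve, the bias is near zero. If ascertainment stopped at Day 64, with exponential durations and uniform onset, true means of 14 and 30 days would be reported as 10.5 and 15.0. Those figures rest wholly on assumed durations and an assumed cut-off. The summary is descriptive and untested, and it has no bearing on the primary endpoint or on the Go/No-Go thresholds in SAP 1.4.

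**What to change.** In SAP 7.1, keep the number and percentage of ocular AEs resolved. Instead of relying on the resolved-only mean, report by arm a descriptive Kaplan-Meier time to resolution for ocular TEAEs, with unresolved events censored at last contact. Beside it, give the number unresolved with their duration so far, separating events judged stable from those refused, lost or still open. State the cut-off for resolution dates, for example database lock. No test is needed, so section 9.5.2 of the protocol is respected.

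The cost is a sentence or two in the SAP and one table, built from onset, resolution and last-contact dates. The downside is imprecision: with perhaps nine events per arm, some clustered within subjects, medians will be unstable and should be presented as such. The display of unresolved events will often be more informative than the curve.

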7.2.2 Collection of Adverse Events

Adverse events that occur between the time subject signs the ICF for the study and the time when that subject is randomized will be summarized as medical history and not as a treatment-emergent adverse event unless the event meets the definition of an SAE or AE related to protocol specific procedures.

Adverse events that occur between the time when subject is randomized and last visit should be reported through CRF. All SAEs should be reported to Harbour BioMed within 24 hours of awareness.

Any SAE between last visit and study completion that has a causal relationship with investigational product should be immediately reported to Harbour BioMed and recorded in CRF.

Post-study AE/SAE that investigators judge its occurrence related to investigational product should be reported to Harbour BioMed PV through spontaneous reporting.

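### The SAP 7.1 rule that keeps AEs with pre-treatment onset out of the summary tables has no exception for later worsening, so it contradicts the TEAE definition; few events, possibly none, are exposed

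*SAP*

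**What the plan says.** SAP section 7.1 opens with the overall AE summary, which is to count AEs, SAEs, TEAEs and serious TEAEs by treatment group. In that paragraph it says "AEs recorded in the eCRF which began prior to treatment will not be included in the summary tables". The same sentence keeps these events in the AE data listings.

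The next paragraph of SAP 7.1 defines a TEAE as "any adverse event that occurs or worsens from the first dose of study treatment (at visit 2) to last dose+7 day". The opening of SAP section 7 gives a similar definition: "which is defined as AE that occur or worsen after the first dose of study treatment".

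Protocol section 9.5.2 has two limbs. An AE is treatment-emergent if it starts after the first randomised dose, or "if it is present prior to receipt of randomized study treatment but worsens in severity or increases in frequency" after that dose.

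Three further protocol rules decide which events the SAP sentence can reach:

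- Section 7.2.2: an AE between consent and randomisation "will be summarized as medical history and not as a treatment-emergent adverse event unless the event meets the definition of an SAE" or is related to protocol-specific procedures.
- Section 7.2.1: an aggravation of an existing condition, or a marked rise in its frequency or intensity, is itself an AE.
- Section 7.2.5: dry eye signs and symptoms provoked by the CAE are not recorded as AEs unless they go beyond what is expected. Disease fluctuation and the drop-tolerance assessment are also kept out.

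**The concern.** The exclusion in SAP 7.1 depends only on when an event began. The TEAE definition in the following paragraph depends on when it began or when it got worse. An event that started in the run-in and worsened on randomised treatment therefore falls under two opposite instructions: count it as a TEAE, and keep it out of the tables.

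Such events can arise. Before the first randomised dose, subjects use open-label placebo drops twice daily from Day -13 to Day 0. They also undergo two 90-minute CAE exposures, with fluorescein staining and Schirmer testing at both visits.

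As written, the exclusion can only lower the TEAE counts. Safety is the secondary objective in protocol section 2.2, and SAP section 1.4 names safety data among the inputs when the primary result falls in the pending range. The AE tables are descriptive, so no test is affected. But with 50 subjects planned per group, each subject missing from an incidence row moves that row by 1/50 = 2 percentage points.

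**Working it through.** The plan states no figure to reproduce, and the documents give no count of events that start before treatment and worsen on it. The check is therefore a comparison of rules. I read treatment in the exclusion sentence as the randomised treatment first given at Visit 2, because SAP 7.1 ties the TEAE definition to that visit.

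**Step 1. Apply both SAP rules to each type of event.**

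| Event | TEAE by SAP 7 and 7.1? | TEAE by protocol 9.5.2? | In the tables under the exclusion sentence? |
|---|---|---|---|
| Starts after first randomised dose | Yes | Yes | Yes |
| Starts before, unchanged afterwards | No | No | No |
| Starts before, worsens in severity, kept under the original onset date | Yes | Yes | **No** |
| Starts before, becomes more frequent, kept under the original onset date | Not stated | Yes | **No** |
| Starts before, worsening entered as a new AE with post-dose onset | Yes | Yes | Yes |

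The third row is a conflict inside SAP 7.1. The fourth is a departure of the SAP from the protocol. In the fifth nothing is lost.

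**Step 2. Which recording rule applies?** Protocol 7.2.1 makes an aggravation an AE, which points towards the fifth row. Neither document says that it receives its own record or a new onset date. If every worsening did, the worsening limb of the SAP definition would have almost nothing to do. The choice between the third and fifth rows is left open.

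**Step 3. Which records can sit in the third or fourth row?**

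1. Under protocol 7.2.2, ordinary events between consent and randomisation become medical history. A later aggravation is then most naturally a new post-dose AE, and is counted.
2. Under protocol 7.2.5, expected CAE-provoked signs never become AE records.
3. What clearly remains as an AE record with a pre-treatment onset is a run-in SAE, or an AE related to study procedures. For the CAE, that means a reaction beyond the expected range.
4. Of these, only events that worsen or become more frequent after the first randomised dose, and keep their original onset date, are affected.

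The exposed set is narrow. It is not empty by rule: the visit instructions in protocol section 8.1.1 ask for AEs to be reported from consent onwards, and the SAP sentence itself presupposes that some eCRF records predate treatment.

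**The case against.** The strongest reply is that the exclusion sentence sits in the paragraph on overall AE counts and serves only to keep untreated events out of them. On that reading the TEAE tables follow the definition in the next paragraph, worsening included. This is a sensible account of what was meant, but the text does not secure it. The sentence refers to the summary tables without limit, and the overall summary in its own paragraph also reports TEAEs and serious TEAEs.

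A second reply is that protocol 7.2.1, 7.2.2 and 7.2.5 leave little for the rule to remove. This stands, and it sets the size of the point. It does not remove the contradiction, because SAEs and procedure-related AEs are exempt from the medical-history rule and no recording convention for a worsening is stated.

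A third reply is that nothing disappears from the report. This also stands: the events remain in the listings, and some ocular worsening would show in the slit-lamp shift tables and in the visual acuity and IOP changes. A reader might infer from the exclusion sentence that genuine TEAEs are lost from the safety results as a whole. The documents support only their absence from the AE summary tables.

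A reader might also try to size the loss from the US phase II study in protocol section 1.4.2: 64 AEs less 51 TEAEs leaves 13, and 13/64 = 20.3%. That is not a valid ceiling. Under the protocol 9.5.2 definition, an event that worsened after first dose would already be among the 51, so the other 13 are not worsening events. The US study's own definition is not given. The figure should not be used.

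**Conclusion.** The contradiction is real and can be read directly from SAP 7.1. The literal rule gives a wrong TEAE count for any pre-treatment AE that worsens after the first randomised dose and is kept under its original onset date. Such an event would appear in the listings but not in the AE summary tables. Separately, the SAP omits the increase-in-frequency limb of the protocol definition.

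The practical effect is probably small. It falls mainly on run-in SAEs and procedure-related AEs, its size cannot be derived from the documents, and it may be zero. It depends on two things the documents leave open: that a worsening stays under its original onset date, and that the tables are programmed as the exclusion sentence reads. The point warrants correction because the rule is wrong as stated and easy to repair, not because a material bias has been shown.

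**What to change.** In SAP 7.1, replace the exclusion with wording such as: *AEs that began before the first randomised dose and did not worsen in severity or increase in frequency afterwards are listed only; those that did are TEAEs and are included in all TEAE tables.*

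Use the two-limb definition of protocol 9.5.2 in both SAP 7 and SAP 7.1. The end of the SAP 7.1 window, seven days after last dose, is not in question here.

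State, in the SAP or the eCRF completion instructions, whether a worsening is recorded as a new AE with its own onset date or as a change to the existing record.

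The cost is a few sentences and one derivation flag, settled before database lock and unblinding. TEAE counts may rise slightly. The efficacy analyses are not touched.
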